7.1.5. Study Period

Adverse events will be classified according to the time of occurrence relative to the study intervention period.

Treatment emergent	Definition
Y	If event start date is not missing and is before date of first dose of study medication.
N	Any event started on or after date of first dose of study medication or event date is missing or partial

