- Patient withdrawal of consent: At any time, a patient's participation in the study may terminate at his/her request. The specific reason for patient withdrawal will be noted on the case report form (CRF).
- Lost to follow-up: The patient stops coming for visits, and study personnel is unable to contact the patient after repeated attempts (e.g., mail, or email).
- This study may be terminated at the discretion of the Sponsor or any regulatory agency.

If a patient's infusions are discontinued at any point during the trial and the patient maintains consent to contribute additional outcome information, the patient should continue to be followed through Week 26 for all safety and efficacy assessments. Investigators will be trained about the importance of retention and steps to prevent missing data.

The date and reason for withdrawal are to be documented in the CRF. The study site must immediately notify the medical monitor. The patients who withdraw prematurely must attend an early discontinuation visit if possible, at which time they will complete all assessments described in Table 2 under the Week 26 visit.

In the event that a patient discontinues prematurely from the study due to an Adverse Event (AE) or serious AE, the event will be followed until it resolves (returns to normal or baseline values) or stabilizes, or until it is judged by the Investigator to be no longer clinically significant. Once a patient is withdrawn from the study, the patient may not re-enter the study.

If the subject develops symptoms associated with COVID-19 during the conduct of this study, they will be asked to consult their personal physician and be tested for COVID-19, and to selfquarantine for at least 14 days. Quarantine must occur while waiting for COVID-19 test results. Once asymptomatic, subject may resume site visits. If the test results are positive, the subject will be asked to quarantine and may continue to receive infusions at the quarantine site. If the subject develops severe symptoms (ie., shortness of breath/difficulty breathing) they should go to the ER instead of personal physician.

Treatments

Details of the investigational product

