For the purposes of this study, the period of observation for collection of AEs extends from the time the patient gives informed consent through Week 26 (or early discontinuation visit). Follow-up of the AE is required until the event resolves or stabilizes at a level acceptable to the Investigator.

Intensity of Adverse Event

The intensity of the AE will be judged based on the following:

Mild	Awareness of sign(s) or symptom(s) which is/are easily tolerated
Moderate	Enough discomfort to cause interference with usual activity
Severe	Incapacitating or causing inability to work or to perform usual activities

Infusion Stopping Rules

Infusion will be stopped when:

- Allergic reaction is aroused after the product has been administered intravenously.
- Patient verbally decline the treatment at any moment prior, or during the infusion.

- Hyperpyrexia develops after infusion administration begins (core body temperature greater than or equal to 40°C) [57].
- PI may stop the study at any time, based upon PI's discretion
- Malignant Hypertension (180/120 mm/Hg)
- Sudden Severe Hypotension (30-40 mm/Hg drop from pre-infusion level)

Study Alteration Rules

If any of the following events listed below occur, administration of the study drug will be immediately suspended. The Internal Monitoring Committee (IMC), presided by the Medical Monitor will meet to review the incident and its etiology. The committee determine if it is likely related to the drug, the infusion or unrelated. If the IMC along with the Medical Monitor agree that the SAE is unlikely or unrelated to the drug, the study will be continued. If the SAE appears to be definitely drug-related, the study will be stopped. If the SAE is probably or possibly linked to the drug, the IMC will determine the risk to future patients and decide if the study should proceed or be stopped.

Study Stopping Rules

The stopping rules listed below will trigger cessation of enrollment and potential study closure pending a comprehensive DSMB safety review.

1. Any infusion related death, deemed by PI to be associated or possibly associated with study drug.
2. Three or more of the same Grade 3 or higher AEs (judged by the investigator, medical monitor or sponsor), including infusion site reactions.
3. Any event which, in the opinion of the investigator, medical monitor or sponsor, contraindicates further dosing of additional subjects.

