5.3.2.1. Adverse Events

AEs will be coded using the most recent version of the Medical Dictionary for Regulatory Activities (MedDRA).

A treatment emergent adverse event (TEAE) is defined as an event that has onset date on or after the first day of exposure to infusion treatment and on or before the last day of infusion treatment. Here the first day of exposure is defined as the first day of exposure to infusion treatment.

Treatment Adverse events (TAES) are summarised descriptively, whereas non-TEAEs are presented in listings. TAE data will be displayed in terms of the number of subjects with at least one event (N), percentage of subjects with at least one event (%) and the number of events (E).

Individual adverse events will be listed.

The details of the planned displays are in programming specification document.

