7.1.3. Prior and Concomitant Medications

Prior and concomitant medications will be coded using WHO Drug Dictionary. Concomitant medications will be summarized as number and percentage of subjects.

For classifying study phase for concomitant medications, use the following definition.

Study Phase	Definition
Prior	If medication end date is not missing and is before date of first dose of study medication.
Concomitant	Any medication that is not a prior

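### SAP 7.1.5 reverses the treatment-emergent flag: events before first dose get Y and events on or after it get N, the opposite of SAP 5.3.2.1

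*SAP*

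**What the plan says.** SAP 7.1.5 (Study Period) is a two-row table. Treatment emergent is Y "If event start date is not missing and is before date of first dose of study medication". It is N for "Any event started on or after date of first dose of study medication or event date is missing or partial".

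SAP 5.3.2.1 (Adverse Events) defines a treatment-emergent adverse event (TEAE) as one with "onset date on or after the first day of exposure to infusion treatment and on or before the last day of infusion treatment". It summarises what it calls treatment adverse events by number of subjects, percentage and number of events, whereas "non-TEAEs are presented in listings". It adds: "Individual adverse events will be listed".

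SAP 7.1.3 classes a medication as prior "If medication end date is not missing and is before date of first dose of study medication".

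The protocol, in its text on serious adverse events, collects adverse events "from the time the patient gives informed consent through Week 26" or the early discontinuation visit. Under Withdrawal, Removal, and Replacement of Patients it says that when infusions are discontinued but consent is maintained, "the patient should continue to be followed through Week 26 for all safety and efficacy assessments".

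**The concern.** The two SAP sections define the same flag in opposite directions, and nothing else in the SAP or protocol reconciles them. An event on the day after the first infusion is treatment emergent under 5.3.2.1 and not treatment emergent under 7.1.5.

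Two features of 7.1.5 point to transposed labels rather than a deliberate rule. The Y row has the wording of the prior-medication rule in 7.1.3, with event start date in place of medication end date. Missing and partial dates fall under N, which is the less cautious side; after a swap they would fall under Y.

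This matters because 5.3.2.1 tabulates one group and only lists the other, and 7.1.5 is the only place in the SAP that sets out a Y/N derivation. A programmer working from it would keep every post-infusion event out of the summary tables. What remained would be events with a known onset between consent and first dose. These may be few: the schedule of assessments (protocol Table 2) marks no adverse event monitoring at screening, although the protocol text starts collection at consent. The trial is single-arm, and the incidence of drug-related adverse events and serious adverse events is a listed secondary endpoint, so the summary counts and percentages carry much of the planned safety result.

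**Working it through.** The plan gives no figure to reproduce. The check classifies each nominal onset day under each rule and compares the flags.

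**Inputs**
- Study day (SAP 7.1.6): the day of first dose is Day 1, later days are date − first dose date + 1, and there is no Day 0.
- Screening: up to 14 days (SAP 2.2), so Days −14 to −1.
- Infusions at Weeks 0, 2, 6, 10 and 14 (SAP 2.2): Days 1, 15, 43, 71 and 99 (for example 14 × 7 + 1 = 99).
- End of study, Week 26: 26 × 7 + 1 = Day 183.
- Visit window ±3 days (protocol Table 2).

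**Rules**
- A (5.3.2.1): Y if 1 ≤ day ≤ last infusion day, otherwise N.
- B (7.1.5 as printed): Y if day < 1, otherwise N; a missing or partial date is N.
- C (7.1.5 with labels swapped): N if day < 1, otherwise Y; a missing or partial date is Y.

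**Flags, five infusions received**

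| Onset | Days | A | B | C |
|---|---|---|---|---|
| Day −14 to −1 | 14 | N | Y | N |
| Day 1 to 99 | 99 | Y | N | Y |
| Day 100 to 183 | 84 | N | N | Y |
| Date missing | – | no rule | N | Y |

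**A against B (the SAP as printed).** The flags are opposite on 14 of 14 pre-dose days and on 99 of 183 post-dose days: 99/183 = 54.1%. They agree, both N, on 84/183 = 45.9%. Rule B gives Y on none of the 183 post-dose days. Moving the last infusion and Week 26 visits within ±3 days gives 96/186 = 51.6% to 102/180 = 56.7%.

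**A against C (labels swapped, nothing else changed).** The conflict on Days −14 to 99 disappears. A new one appears on Days 100 to 183: 183 − 99 = 84 days, or 12 weeks (180 − 102 = 78 to 186 − 96 = 90 days with the windows). Rule A ends at the last infusion, while the rows of 7.1.5 state no end.

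If the last day of infusion treatment means the patient's own last infusion, the gap widens for patients who stop infusions early and are followed to Week 26:

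| Infusions received | Last infusion day | Days in conflict, A against C |
|---|---|---|
| 4 | 71 | 183 − 71 = 112 |
| 3 | 43 | 183 − 43 = 140 |
| 2 | 15 | 183 − 15 = 168 |
| 1 | 1 | 183 − 1 = 182 |

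**The case against.** The strongest reply is that this is a drafting slip with a conditional consequence. Section 5.3.2.1 sits in the analysis section and has the direction right. Section 7.1.5 is supporting documentation, and its printed result contradicts the term it defines, so a programmer would probably notice. Display details are deferred to a programming specification not available here, and every event is listed individually in any case. This stands as a limit on the harm: it is not known which section programming follows, and the record of events is not lost. It does not justify leaving two opposite definitions in a plan.

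The link from flag to table is also partly inferred. Section 5.3.2.1 says that treatment adverse events (TAES) are summarised, a term the SAP does not define, and 7.1.5 does not say that its flag drives those tables. The inference is reasonable, because the same sentence contrasts these events with non-TEAEs.

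The disagreement on where the window ends changes no flag in the SAP as printed; it appears only once the labels are swapped. The lead-in to 7.1.5 refers to the study intervention period, which may imply an upper limit. The last day of infusion treatment could also mean the end of the planned 14-week treatment period, in which case the conflict for early stoppers falls back to 84 days. These are fair points. The window end is a caution about the repair and not further evidence of the reversal.

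Finally, the day counts are not event counts, and Week 0 has its own ±3-day window, so 14 pre-dose days is a nominal figure. Both points stand, and neither affects the direction of the error.

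**Conclusion.** The concern holds and must be fixed. As printed, 7.1.5 reverses the treatment-emergent flag and contradicts 5.3.2.1 on every nominal onset day from screening to the last infusion (Days −14 to 99). If followed, it would remove all post-infusion events from the TEAE summaries. Confidence in the textual contradiction is high. The effect on the tables depends on programming following 7.1.5 and on its flag selecting the tabulated events.

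The size is given in onset days on the nominal schedule: 54% of post-dose days have opposite flags (52% to 57% with visit windows), and on the rest both sections give N. The documents give no adverse event rates, so the number of events affected cannot be estimated.

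**What to change.** 1. Swap the labels in 7.1.5. N applies only when onset is known to be before first dose. Y applies to onset on or after first dose and to missing or partial dates. State that the known part of a partial date, or the stop date, may establish pre-dose onset, so that no event meets both rows.
2. Use one definition in 5.3.2.1 and 7.1.5, with an explicit end to the window. Either keep the last-infusion end and write it into 7.1.5, saying whether it means the patient's own last infusion or the end of the planned treatment period; or extend 5.3.2.1 to Week 26 to match the adverse event collection period. If the window is extended, declare the change and show events up to and after the last infusion separately, so that results under the 5.3.2.1 window remain readable.
3. In 5.3.2.1, replace the undefined term TAES with TEAE, and bring the programming specification into line.

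The cost is wording and programming; no new data are needed. Extending to Week 26 would add to the TEAE counts any events starting in the roughly 12 weeks after the last infusion, or longer for patients who stop infusions early. Keeping the last-infusion end leaves those events in listings only. Under either option, missing or partial dates that cannot be shown to be pre-dose would count as treatment emergent.

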7.1.6. Study Day and Reference Dates

Study Day

• Study Day 1 is defined as the day the first dose was taken.• Study day >1 is calculated as the number of days from the date of the Study Day 1:
• Ref Date = Missing → Study Day = Missing• Ref Date < Date of Study Day 1 → Study Day = Ref Date – Date of Study Day 1• Ref Date ≥ Date of Study Day 1 → Study Day = Ref Date – (Date of Study Day 1) + 1

7.1.7. Assessment Window

For data summaries by visit, scheduled visits with nominal visit description will be displayed. Unscheduled visits will not be displayed or slotted into a visit window. While in the baseline derivation or post-baseline worst scenarios are derived, unscheduled visits are considered. All unscheduled visits will be displayed in listings, as appropriate.

7.1.8. Multiple measurements at One Analysis Time Point

For lab tests on a study day, if more than one assessment is taken on the same day, the test from the latest non-missing lab measurements will be used for the analysis. All lab measurements will be displayed in the listings, as appropriate.

